Ethics Committee approval was obtained at all study centres before commencement of the trial, and all patients provided informed consent. All relevant factors were recorded on a trial case report form (CRF).

ERAS perioperative care principles were emphasised. All patients received prophylactic antibiotics according to established guidelines. Medications were mostly continued perioperatively unless or at the clinicians discretion, but we recommended withholding ACE-inhibitors and ARBs on the day of surgery. We recorded preoperative use of bowel preparation, fasting times, ERAS data, medications, and biochemistry and haematology results on the CRF. Choice of anaesthetic agents and perioperative analgesia were left to the discretion of the anaesthetist; such data were recorded.

The acceptable limits of low BP, and a definition of ‘hypotension’, vary widely.²⁹ We used a general guideline of systolic BP <90 mmHg for more than 5 mins, but also asked the attending anaesthetist to modify their acceptable lower limit of sBP at the commencement of surgery, and, according to randomly-assigned group, treat hypotension with additional IV fluid or vasopressor therapy. Such modifications to the acceptable lower sBP were recorded.

Patients were followed daily and outcomes were recorded until hospital discharge. We recommended that antihypertensive medications should be withheld until sBP was consistently at or above preoperative levels. Serum electrolytes, Hb/haematocrit, and a 12-lead ECG were ordered preoperatively and on Day 1 after surgery. CRP was measured on postoperative Day 3 and whenever sepsis was suspected. Additional laboratory tests were ordered if clinically indicated. On Day 3 all patients completed the 15-item quality of recovery score (QoR-15).³⁰

On Day 30 all patients were contacted by phone to ascertain if they have experienced any outcomes, and if detected, further testing was arranged. The QoR-15 was repeated on Day 30 along with World Health Organization Disability Assessment Schedule 2.0 (WHODAS), and the WHODAS was repeated at 3-, 6- and 12-month follow-up to ascertain survival status and new-onset disability.³¹

Outcomes

There is a need for patient-centered outcome assessments in the study of perioperative anaemia.^{32 25}

Primary Endpoint

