Persistent disability or death by 90 days, where persistent disability was defined as a WHODAS 2.0 score of at least 24 points (on the 48-point scale) at both 30 days and 90 days post-operatively,³¹ reflecting a disability level of at least 25% and being the threshold point between “disabled” and “not disabled” as per WHO guidelines.³³ Disability was assessed by the participant, but if unable then we used the proxy’s report.

Secondary Endpoints

Secondary endpoints include an *a priori* composite of 30-day mortality or major septic complications (sepsis, surgical site infection, anastomotic leak, and pneumonia), plus each individually, blood transfusion, acute kidney injury, ICU and hospital stay, unplanned admission to ICU, and quality of recovery (QoR-15).³⁰ We used the following definitions:

1. Death: all-cause mortality at 90 days, then up to 12 months after surgery
2. A composite (pooled) and individual septic complications: sepsis, surgical site infection, anastomotic leak, and pneumonia
3. Sepsis: using Centers for Disease Control and Prevention (CDC) with National Healthcare Safety Network (NHSN) criteria³⁴
4. Surgical site infection: using CDC criteria³⁴

5. Pneumonia: The presence of new and/or progressive pulmonary infiltrates on chest radiograph plus two or more of the following:
 - i. Fever $\geq 38.5^{\circ}\text{C}$ or postoperative hypothermia $<36^{\circ}\text{C}$
 - ii. Leucocytosis $\geq 12,000 \text{ WBC}/\text{mm}^3$ or leucopenia $< 4,000 \text{ WBC}/\text{mm}^3$
 - iii. Purulent sputum and/or
 - iv. New onset or worsening cough or dyspnoea.
6. Anastomotic leak: A defect of the intestinal wall at the anastomotic site (including suture and staple lines of neorectal reservoirs) leading to a communication between the intra- an extra luminal compartments.
7. Acute kidney injury: according to The Kidney Disease: Improving Global Outcomes (KDIGO) group criteria, but not urine output – for Stage 2 or worse AKI defined as at least 2-fold increase in creatinine, or estimated GFR decrease $>50\%$ ³⁵. We also plan to report renal replacement therapy up to 90 days after surgery
8. Unplanned admission to ICU within 30 days of surgery
9. Total ICU stay: additive, including initial ICU admission and readmission times up to Day 30
10. Hospital stay: additive, from the start (date, time) of surgery until actual hospital discharge , plus readmission(s) up to Day 30
11. Quality of recovery: QoR-15 score³⁰ on Days 3 and 30

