All statistical analysis will be done by [name] (biostatistician). Our initial sample size calculation was based primarily on our own data and other published studies.^{38,39} This resulted in a final sample size of 3,000 that provided 80% power for the trial.⁵ We plan to analyse the intention-to-treat population of the RELIEF trial.⁵

Descriptive statistics will be used to compare the baseline characteristics of patients with and without post-operative anaemia on Day 3, hereafter titled 'anaemia groups'. The binary primary outcome, persistent disability or death to 90 days, will be compared between anaemia groups using log-binomial regression to estimate risk ratios and 95% confidence intervals directly, adjusting for RELIEF randomised group, age, sex, ASA physical status, Charlson score, preoperative aspirin, haemoglobin, type of surgery, planned HDU/ICU (either), and duration of surgery. Further possible confounders will be determined prior to commencement of the statistical analysis. Should the log-binomial model fail to converge, modified Poisson regression with robust standard errors will be used. Other binary endpoints will be analysed similarly. Duration of stay outcomes will be summarised using medians and interquartiles ranges, and compared across anaemia groups using accelerated failure time models with adjustment for the same factors. QoR-15 scores will be summarised using medians and interquartiles ranges, and compared across anaemia groups using median regression.

To assess the secondary aim, the risk of postoperative anaemia at Day 3 will be compared between RELIEF randomised arms using proportions and analysis using (unadjusted) log binomial regression.

Baseline and pre-Day 3 characteristics of patients missing the Day 3 anaemia assessment will be compared with those who have the measurement present. If there is evidence of missing Day 3 anaemia being dependent on these characteristics then multiple imputation of Day 3 anaemia will be performed using chained equations, including baseline and post-baseline variables, including the relevant outcome variables in the imputation models.

Exploratory subgroup analyses will be done for persistent disability or death to 90 days, acute kidney injury, Day 3 QoR-15, and hospital stay according to (i) RELIEF randomised group, (ii) the presence of preoperative anaemia, and (iii) receipt of a red cell transfusion. These will be reported as a web-supplement.

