IV fluids (total volume) will be tabulated according to reporting in the RELIEF trial, for intraoperative plus recovery room (combined), and Days 1, 2 and 3.

Daily weight and CRP (if done) on Day 3 will be reported as mean (SD).

STATISTICAL ANALYSES

All statistical analysis will be performed with the intention-to-treat population of the RELIEF trial.⁵

Descriptive statistics will be used to compare the baseline and pre-Day 3 characteristics of patients with and without post-operative anaemia on Day 3, hereafter titled 'anaemia groups'.

The binary primary outcome, persistent disability or death to 90 days, will be compared between anaemia groups using log-binomial regression to estimate risk ratios and 95% confidence intervals directly, adjusting for RELIEF randomised group, age, sex, ASA physical status, Charlson score, preoperative aspirin, haemoglobin (baseline), type of surgery, planned HDU/ICU (either), and duration of surgery. Should the log-binomial model fail to converge, modified Poisson regression with robust standard errors will be used. Methods for addressing missing Day 3 anaemia are provided below.

Other binary endpoints (#1-8, 12) will be analysed similarly. Duration of stay outcomes (#9,10) will be summarised using medians and interquartiles ranges, and compared across anaemia groups using parametric accelerated failure time models with adjustment for the same factors. QoR-15 scores (#11) will be summarised using medians and interquartiles ranges, and compared across anaemia groups using median regression with robust standard errors.

To assess the secondary aim, the risk of postoperative anaemia at Day 3 will be compared between RELIEF randomised arms using proportions and analysis using log binomial regression adjusted for planned ICU/HDU admission.

Baseline and pre-Day 3 characteristics of patients missing the Day 3 anaemia assessment will be compared with those who have the measurement present. If there is evidence of missing Day 3 anaemia being dependent on these characteristics then multiple imputation of Day 3 anaemia will be performed using chained equations, including baseline and post-baseline variables predictive of either Day 3 anaemia being missing or of Day 3 anaemia itself (defined by correlation ≥ 0.30 for either), including the relevant outcome variables in the imputation models.

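### Death to 12 months is analysed as a yes/no outcome, so follow-up that ends with the patient known alive at 3 or 6 months cannot be used as such; the likely effect is small

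*Protocol*

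**What the plan says.** Item 1 of the secondary endpoints reads the same in both documents: "Death: all-cause mortality at 90 days, then up to 12 months after surgery". The Protocol (Statistical Analysis) says only "Other binary endpoints will be analysed similarly", without naming the endpoints meant. The SAP (Statistical Analyses) does name them: "Other binary endpoints (#1-8, 12) will be analysed similarly". Death, item 1, therefore follows the primary-outcome method, "log-binomial regression to estimate risk ratios and 95% confidence intervals directly", with modified Poisson regression if that model does not converge. The SAP does not separate death at 90 days from death to 12 months.

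On how survival is learnt, the Protocol (Study Procedures) states that "the WHODAS was repeated at 3-, 6- and 12-month follow-up to ascertain survival status and new-onset disability".

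Two further passages show what the plan leaves out. The missing-data paragraph of the SAP deals with the exposure: "multiple imputation of Day 3 anaemia will be performed using chained equations", with outcomes entering as predictors. Models for time data are named only for ICU and hospital stay: "Duration of stay outcomes (#9,10) will be summarised using medians and interquartiles ranges", followed by accelerated failure time models. Neither document gives a censoring rule, a rule for unknown 12-month status, a survival model for death, or another source of vital status such as registry linkage.

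**The concern.** A patient reached at 6 months but not at 12 is known to have survived half the period. A log-binomial or modified Poisson model, as specified, needs a yes or a no at 12 months. With no other method in the plan, the analyst either leaves the patient out or codes the patient as alive.

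Leaving out is asymmetric: patients who died before the missed contact stay in, while patients who survived the same months go out. Coding as alive ignores deaths after the last contact. Anaemia is not randomised, and the study hypothesis is that anaemic patients recover worse, so unequal loss between the groups is plausible. At stake are the absolute 12-month mortality figures and, if loss is unequal, the 12-month risk ratio. The choice between the two codings is also left open in the plan.

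**Working it through.** **The plan's own figure.** The only related number is in the Protocol: "This resulted in a final sample size of 3,000 that provided 80% power for the trial". It belongs to the parent trial and comes with no alpha, event rate or effect size, so it cannot be reproduced. With 1,500 per arm and an assumed two-sided 5% level, 80% power fits many pairs of risks (10% v 7.1%, 20% v 16.1%, 35% v 30.2%). Nothing below depends on it.

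**Inputs, all assumed.** The documents give no 12-month mortality and no loss. Take true 12-month mortality p = 8% in anaemic and 5% in non-anaemic patients, a risk ratio (RR) of 0.08/0.05 = 1.60. Half the deaths fall before the 6-month contact, and a share l of those alive at 6 months is lost afterwards, independently of death.

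**Formulas.**
- Early deaths: e = p/2.
- Still followed after 6 months: r = (1 − e)(1 − l).
- Late deaths observed: d = r × (p/2)/(1 − e).
- Lost patients dropped: risk = (e + d)/(e + r).
- Lost patients counted alive: risk = e + d.
- Censored at 6 months (Kaplan-Meier): risk = 1 − (1 − e)(1 − d/r), which equals p.

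**Worked case, loss 15% v 5%.**
- Anaemic: e = 0.04; r = 0.96 × 0.85 = 0.816; d = 0.816 × 0.04/0.96 = 0.034. Dropped: 0.074/0.856 = 8.64%. Counted alive: 7.40%.
- Non-anaemic: e = 0.025; r = 0.975 × 0.95 = 0.92625; d = 0.92625 × 0.025/0.975 = 0.02375. Dropped: 0.04875/0.95125 = 5.12%. Counted alive: 4.88%.
- RR: 1.69 if dropped, 1.52 if counted alive.
- Kaplan-Meier, anaemic: 1 − 0.96 × (1 − 0.034/0.816) = 8.0%. The non-anaemic risk is likewise 5.0%, so the RR is 1.60.

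| Loss, anaemic v non-anaemic | Dropped | RR | Counted alive | RR | Kaplan-Meier RR |
|---|---|---|---|---|---|
| 10% v 10% | 8.41% v 5.26% | 1.60 | 7.60% v 4.75% | 1.60 | 1.60 |
| 15% v 5% | 8.64% v 5.12% | 1.69 | 7.40% v 4.88% | 1.52 | 1.60 |
| 5% v 10% | 8.19% v 5.26% | 1.56 | 7.80% v 4.75% | 1.64 | 1.60 |

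With equal 10% loss, dropping puts both absolute risks about 5% too high in relative terms (8.41/8 and 5.26/5), and counting alive puts them 5% too low.

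**Second model as a check.** Assume a constant hazard, with loss split equally after the 3- and 6-month contacts and true risks of 10% v 5% (RR 2.00). Equal loss of 2% to 10% keeps the RR between 1.997 and 2.001. Loss of 10% v 2% gives 2.06 if dropped and 1.90 if counted alive. Censoring gives 2.00 throughout. The directions agree with the table.

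**Set against sampling error.** Assume 1,500 patients per anaemia group at 8% and 5%, that is 120 and 75 deaths. The unadjusted standard error of log RR is √(1/120 − 1/1500 + 1/75 − 1/1500) = 0.14, and the 95% interval around 1.60 is roughly 1.2 to 2.1. The shift from 1.60 to 1.69 is about 0.05 on the log scale, and 0.05/0.14 is a little over a third of a standard error.

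**The case against.** Risk of death at a fixed time is a legitimate estimand and matches the scale of the other binary endpoints. This stands, and the fix keeps that scale.

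A reader might infer that the yes/no form forces the analyst to drop patients or assume them alive. It does not: outcome imputation or inverse-probability weighting would also serve a binary endpoint. The plan provides neither, since its imputation is for Day 3 anaemia, so the two crude routes are what remains as written and not a logical necessity.

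A reader might also infer that dropping always overstates mortality. That needs loss to be unrelated to death. If patients cannot be reached because they have died, dropping them can understate mortality, and a censored analysis is then biased as well. The Kaplan-Meier column reproduces the true ratio because independent loss is built into the scenarios; it is not evidence about this cohort.

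No loss is documented. Staged contacts show that follow-up could end early, not that it did. The Protocol mentions survival status at contacts and does not say that dates of death are held. These objections limit the size and certainty of the point without removing it.

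Finally, readmission at 12 months (item 12) sits in the same binary list and depends on the same late follow-up. That is fair, and argues for a general statement on incomplete outcomes as well.

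**Conclusion.** The point holds in a limited form. The SAP analyses death to 12 months by a model that cannot use partial follow-up, and the plan has no method for outcomes with incomplete follow-up. If loss is independent of death within groups, dropping overstates and counting alive understates absolute 12-month mortality. The risk ratio is noticeably biased only if loss differs between anaemia groups.

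The size is unknown because the extent of loss is not reported, and it is probably small: in the most unequal scenario in the table, 1.60 becomes 1.69 or 1.52, well inside sampling error. The documents do not support reading this as a demonstrated bias in the 12-month result. Death at 90 days is exposed only where the 3-month contact is missed. This is a worthwhile refinement of one time point of a secondary endpoint.

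**What to change.** In the SAP, Statistical Analyses:
- Keep log-binomial regression for death at 90 days.
- Take death to 12 months out of the binary list. Analyse it as time to death, censored at the last known-alive contact, with the same covariates.
- Report Kaplan-Meier 12-month risks by anaemia group and an adjusted 12-month risk ratio, from pseudo-observations or a standardised Cox model.
- First confirm whether dates of death are held. If only status at each contact is available, use a discrete-time model over the contact intervals.
- Report the number with unknown 12-month status in each anaemia group.

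The cost is SAP wording and one extra model. That model assumes independent censoring, and proportional hazards if Cox is chosen; pseudo-observations avoid the latter. With complete follow-up, the unadjusted 12-month risks are the same as under the present plan.

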Association of Postoperative Anaemia with Patient Outcome in the RELIEF Trial

ClinicalTrials.gov Identifier: NCT04978285

Statistical Analysis Plan

28 September, 2021

BACKGROUND

Both preoperative anaemia and red cell transfusion are independent risk factors in major surgery. Patient blood management (PBM) aims to reduce the need for blood transfusion in an effort to improve patient outcomes. Australian PBM guidelines for the surgical patient are available, but there is no specific PBM guidance on the treatment of *postoperative* anaemia.

The consequences of *postoperative* anaemia remain unclear. Postoperative anaemia is more likely if there is pre-existing anaemia, but also increased perioperative blood loss, frequent blood sampling, excess IV fluids (leading to haemodilution), sepsis, and inadequate nutritional intake after surgery. A nadir in Hb concentration is most often observed within the first 3–4 days after surgery. Postoperative anaemia is believed to have deleterious effects on patient outcomes, including prolonged hospital stay, increased postoperative complications, and perhaps poor survival, but there is very little data to support this belief.

We therefore propose a study to investigate the incidence, extent, and outcomes of patients with anaemia after major surgery, including an assessment of the amount of IV fluids administered in the immediate perioperative period.

STUDY AIMS AND HYPOTHESES

Primary aim - To investigate the relationship between postoperative anaemia and patient-centred outcomes after major abdominal surgery.

Secondary aim – To determine whether a more liberal perioperative IV fluid strategy increases the risk of postoperative anaemia (haemodilution) at Day 3.

Hypothesis: Adults with anaemia in the immediate postoperative period following major abdominal surgery have a poorer quality of recovery and higher risk of complications, leading to poor disability-free survival when compared with patients without postoperative anaemia.

STUDY DESIGN

A cohort study comparing patients with and without postoperative anaemia, using prospective data collected in a large, pragmatic, multicentre, randomized trial, the RELIEF trial, in which patients were randomly assigned to either a restrictive (zero balance) or liberal IV fluid regimen, stratified by site and planned HDU/ICU admission.⁵ The intention-to-treat population of the RELIEF trial will be utilised, namely all participants who were enrolled, randomised and underwent induction of general anaesthesia for eligible surgery.

Inclusion and exclusion criteria are as for the RELIEF trial.⁵

GROUP AND ENDPOINT DEFINITIONS

ANAEMIA GROUP DEFINITION

Postoperative anaemia will be defined according to the World Health Organisation definition (males Hb <130 g/L, and female Hb <120 g/L), as measured on postoperative Day 3, using the “Lowest Haemoglobin concentration”. Patients with missing Day 3 haemoglobin data will have these values imputed rather than these patients being excluded (details below).

A secondary group definition will be studied defined as patients with severe anaemia (Hb <100 g/L) at day 3 postoperatively.

LIBERAL PERIOPERATIVE IV FLUID GROUP DEFINITION

Liberal and restrictive perioperative IV fluid groups are defined as the corresponding randomised arms of the RELIEF trial. In brief, Liberal protocol group received a bolus of Hartmann’s balanced salt crystalloid 10 ml/kg at the commencement of surgery followed by 8 ml/kg/h administered until the end of surgery, and then maintenance infusion continued at 1.5 ml/kg/h for at least 24 hours. Patients assigned to the Restrictive protocol group received approximately half of this IV fluid volume.⁵

ENDPOINT DEFINITIONS

Primary endpoint

Persistent disability or death by 90 days, where persistent disability was defined as a WHODAS 2.0 score of at least 24 points (on the 48-point scale) at both 30 days and 90 days post-operatively,³¹ reflecting a disability level of at least 25% and being the threshold point between “disabled” and

“not disabled” as per WHO guidelines.³³ Disability was assessed by the participant, but if unable then we used the proxy’s report.

Secondary endpoints

Secondary endpoints include an *a priori* composite of 30-day mortality or major septic complications (sepsis, surgical site infection, anastomotic leak, and pneumonia), plus each individually, acute kidney injury, ICU and hospital stay, unplanned admission to ICU, hospital readmission and quality of recovery (QoR-15).³⁰ We used the following definitions:

1. Death: all-cause mortality at 90 days, then up to 12 months after surgery
2. A composite (pooled) and individual septic complications: sepsis, surgical site infection, anastomotic leak, and pneumonia. [Detailed clinical definitions are provided in the Protocol]
3. Sepsis: using Centers for Disease Control and Prevention (CDC) with National Healthcare Safety Network (NHSN) criteria³⁴
4. Surgical site infection: using CDC criteria³⁴
5. Pneumonia: The presence of new and/or progressive pulmonary infiltrates on chest radiograph plus two or more of the following:
 - i. Fever $\geq 38.5^{\circ}\text{C}$ or postoperative hypothermia $<36^{\circ}\text{C}$
 - ii. Leucocytosis $\geq 12,000 \text{ WBC}/\text{mm}^3$ or leucopenia $< 4,000 \text{ WBC}/\text{mm}^3$
 - iii. Purulent sputum and/or
 - iv. New onset or worsening cough or dyspnoea.
6. Anastomotic leak: A defect of the intestinal wall at the anastomotic site (including suture and staple lines of neorectal reservoirs) leading to a communication between the intra- an extra luminal compartments.
7. Acute kidney injury: according to The Kidney Disease: Improving Global Outcomes (KDIGO) group criteria, but not urine output – for Stage 2 or worse AKI defined as at least 2-fold increase in creatinine, or estimated GFR decrease $>50\%$ ³⁵.
We will also report renal replacement therapy up to 90 days after surgery
8. Unplanned admission to ICU within 30 days of surgery
9. Total ICU stay: additive, including initial ICU admission and readmission times up to Day 30
10. Hospital stay: additive, from the start (date, time) of surgery until actual hospital discharge , plus readmission(s) up to Day 30
11. Quality of recovery: QoR-15 score³⁰ on Days 3 and 30
12. Hospital re-admission at 3, 6 and 12 months

PROCESS DATA CALCULATIONS

Red cell transfusions will be reported as dichotomous data (yes/no, where yes is any red cell volume $\geq 1 \text{ ml}$) data, and calculated for the intraoperative period plus recovery room (combined), and postoperative Days 1, 2 and 3.

IV fluids (total volume) will be tabulated according to reporting in the RELIEF trial, for intraoperative plus recovery room (combined), and Days 1, 2 and 3.

Daily weight and CRP (if done) on Day 3 will be reported as mean (SD).

STATISTICAL ANALYSES

All statistical analysis will be performed with the intention-to-treat population of the RELIEF trial.⁵

Descriptive statistics will be used to compare the baseline and pre-Day 3 characteristics of patients with and without post-operative anaemia on Day 3, hereafter titled 'anaemia groups'.

The binary primary outcome, persistent disability or death to 90 days, will be compared between anaemia groups using log-binomial regression to estimate risk ratios and 95% confidence intervals directly, adjusting for RELIEF randomised group, age, sex, ASA physical status, Charlson score, preoperative aspirin, haemoglobin (baseline), type of surgery, planned HDU/ICU (either), and duration of surgery. Should the log-binomial model fail to converge, modified Poisson regression with robust standard errors will be used. Methods for addressing missing Day 3 anaemia are provided below.

Other binary endpoints (#1-8, 12) will be analysed similarly. Duration of stay outcomes (#9,10) will be summarised using medians and interquartiles ranges, and compared across anaemia groups using parametric accelerated failure time models with adjustment for the same factors. QoR-15 scores (#11) will be summarised using medians and interquartiles ranges, and compared across anaemia groups using median regression with robust standard errors.

To assess the secondary aim, the risk of postoperative anaemia at Day 3 will be compared between RELIEF randomised arms using proportions and analysis using log binomial regression adjusted for planned ICU/HDU admission.

Baseline and pre-Day 3 characteristics of patients missing the Day 3 anaemia assessment will be compared with those who have the measurement present. If there is evidence of missing Day 3 anaemia being dependent on these characteristics then multiple imputation of Day 3 anaemia will be performed using chained equations, including baseline and post-baseline variables predictive of either Day 3 anaemia being missing or of Day 3 anaemia itself (defined by correlation ≥ 0.30 for either), including the relevant outcome variables in the imputation models.

Exploratory subgroup analyses will be done for persistent disability or death to 90 days, acute kidney injury, Day 3 QoR-15, and hospital stay according to (i) RELIEF randomised group, (ii) the presence of preoperative anaemia, and (iii) receipt of a red cell transfusion. These will be reported as a web-supplement.

Secondary analyses of those with and without more marked anaemia (Hb <100 g/L) will be undertaken for the primary outcome (persistent disability or death to 90 days), plus Day 3 QoR-15 score and hospital re-admissions at 3 months.

REFERENCE

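### Patients who die before postoperative Day 3 have no Day 3 haemoglobin, yet the SAP keeps them in the anaemia comparison, would impute their group and has no exception for them

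*SAP*

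**What the plan says.** Five statements in the SAP bear on this point.

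- **Entry (Study Design).** The population is "all participants who were enrolled, randomised and underwent induction of general anaesthesia for eligible surgery". Statistical Analyses applies it throughout: "All statistical analysis will be performed with the intention-to-treat population of the RELIEF trial".
- **Exposure (Anaemia Group Definition).** WHO anaemia is judged from haemoglobin "as measured on postoperative Day 3, using the “Lowest Haemoglobin concentration".
- **Missing exposure, group definition.** "Patients with missing Day 3 haemoglobin data will have these values imputed rather than these patients being excluded (details below".
- **Missing exposure, Statistical Analyses.** "If there is evidence of missing Day 3 anaemia being dependent on these characteristics then multiple imputation of Day 3 anaemia will be performed". The method is chained equations, "including the relevant outcome variables in the imputation models". The Protocol's Statistical Analysis section carries the same condition.
- **Endpoint.** The primary endpoint is "Persistent disability or death by 90 days". All-cause mortality at 90 days and up to 12 months is a separate secondary endpoint. Neither has a start of follow-up at Day 3.

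Neither document sets a Day 3 landmark, requires survival to Day 3, or separates a haemoglobin that was not taken from one that could not exist.

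**The concern.** Imputation fills in a value that existed but was not recorded. For a patient who died in theatre or on Days 0 to 2, no Day 3 value ever existed. Putting the outcome in the model is sound practice when a covariate is missing in a living patient. Here the outcome came before the exposure and prevented it, so the model would derive the patient's group partly from the death itself and then count that death as an event in that group.

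The study hypothesis is that postoperative anaemia leads to worse disability-free survival. A death before Day 3 cannot inform that hypothesis for an exposure defined on Day 3. The same gap reaches the mortality endpoints and the Hb <100 g/L analysis. It also reaches the secondary aim, where Day 3 anaemia is the outcome of a randomised comparison and imputation would create an outcome for patients who had died.

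**Working it through.** **1. Following one patient through the plan.** A patient is induced, and so is in the population. The patient dies on Day 1, and so has no Day 3 haemoglobin. Under the group definition the patient is kept and imputed. Under Statistical Analyses there are two branches:

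- If missingness is found to depend on patient characteristics, the group is imputed with the outcome among the predictors.
- If it is not, no method is given. A complete-case analysis would drop this patient, together with every living patient without a Day 3 value, which contradicts the group definition.

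On the first branch the death counts as an event in a generated group. On the second, the plan does not say what happens.

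**2. The plan's own figures.** The only stated figures are the parent trial's 3,000 patients and 80% power (Protocol, Statistical Analysis). No event rates or effect size accompany them, so they cannot be reproduced, and this point does not depend on them. The number of early deaths, the anaemia prevalence and the event risks are not given. What follows is illustration on assumed inputs, without covariate adjustment.

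**3. Primary endpoint.** Assumed: N = 3,000; k = 3, 15 or 30 deaths before Day 3; anaemia prevalence p = 60% or 80%; primary event risk 10% or 20%; risk ratio among Day 3 survivors 1.50.

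- Survivors: n = 3,000 − k, n_A = p·n, n_N = n − n_A.
- Later events: E = 3,000 × risk − k.
- Risk in the non-anaemic: r = E/(n_N + 1.5·n_A), so events are a = 1.5·r·n_A and b = r·n_N.
- Adding the early deaths with a fraction s called anaemic: RR = [(a + ks)/(n_A + ks)] / [(b + k(1−s))/(n_N + k(1−s))].

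Outcome-informed imputation would tend towards s = a/(a + b), the split seen in the other events.

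Worked case, k = 15, p = 80%, risk 10%: n_A = 2,388, n_N = 597, E = 285, r = 285/4,179 = 0.0682, a = 244.3, b = 40.7, s = 0.857. Then RR = (257.1/2,400.9)/(42.9/599.1) = 1.497. All called anaemic: (259.3/2,403)/(40.7/597) = 1.58. None called anaemic: (244.3/2,388)/(55.7/612) = 1.12.

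| k = 15 | Split as other events | All anaemic | None anaemic |
|---|---|---|---|
| risk 10%, p 60% | 1.497 | 1.60 | 1.30 |
| risk 10%, p 80% | 1.497 | 1.58 | 1.12 |
| risk 20%, p 60% | 1.497 | 1.54 | 1.40 |
| risk 20%, p 80% | 1.497 | 1.54 | 1.30 |

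Over all assumed k, p and risks, the split result is 1.494 to 1.499.

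**4. Mortality alone.** Assumed: 2,400 anaemic and 600 non-anaemic patients (denominators held fixed), 90 deaths by 90 days, of which 10 are later deaths in the non-anaemic group. RR = (anaemic deaths/2,400)/(non-anaemic deaths/600).

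| Deaths before Day 3 | Later deaths, anaemic/non-anaemic | RR, later deaths only | Early deaths split as later | All anaemic | None anaemic |
|---|---|---|---|---|---|
| 3 | 77/10 | 1.925 | 1.925 | 2.0 | 1.48 |
| 6 | 74/10 | 1.85 | 1.85 | 2.0 | 1.16 |
| 9 | 71/10 | 1.775 | 1.775 | 2.0 | 0.93 |

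The proportional split leaves the ratio of deaths, and hence the RR, unchanged. If each early death is drawn independently at that split, the chance that all are drawn non-anaemic in one imputation is (10/87)³ = 0.15% for three deaths and (10/81)⁹, about 7 in a billion, for nine.

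With the step 3 formula and a rarer endpoint (risk 2%, 60 deaths, k = 15, so 25% of events), the split RR is 1.497. The extremes are 2.07 to 2.20 (all anaemic) and 0.46 to 0.73 (none anaemic).

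**The case against.** The strongest reply is that the plan's own method does little numerical harm. If early deaths are imputed from the pattern in other events, they reproduce the association already present, as steps 3 and 4 show, and multiple imputation averages over draws. This stands. A reader might infer from the extreme columns that a handful of early deaths could reverse the mortality result or seriously bias the primary one. The documents do not support that: they give no count of such deaths, and the extremes are not what the planned imputation would tend to produce.

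A second reply is that such deaths should be few. The Protocol's eligibility criteria require elective surgery and exclude urgent surgery and ASA 5. Its Study Procedures list routine haemoglobin only preoperatively and on Day 1, so many missing Day 3 values may belong to living patients. This is plausible. It supports imputing for the living and gives no reason to impute for the dead.

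Third, a reader might infer that every missing value will be imputed and exclusion is forbidden outright. The group definition reads that way, but Statistical Analyses makes imputation conditional. The documents therefore support only that the two sections disagree and that neither makes an exception for early death.

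Fourth, the generated group would not rest on death alone. Baseline and post-baseline predictors with correlation of at least 0.30 also enter, and a Day 1 haemoglobin could qualify. That improves the prediction, but the quantity predicted is still one that never existed. Including the outcome in the imputation model is not in itself a fault.

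**Conclusion.** The fault is in the definition and follows from the text. The SAP would assign a Day 3 exposure to patients who could not have one, after their event had occurred, and count those events in the primary and mortality comparisons. They carry no information about Day 3 anaemia. The two statements on missing Day 3 haemoglobin also conflict.

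The expected numerical effect is small. Assuming that imputed groups follow the split in the other events, a primary risk ratio of 1.50 moves to about 1.49 to 1.50. If nobody died before Day 3, there is no effect. The wide figures (0.93 to 2.0 for mortality in step 4) show only how far the estimate depends on an assignment that cannot be verified. That dependence is greatest where events are few. The change is worth making before analysis because it is cheap and leaves the exposure definable for every patient compared, not because a large bias has been shown.

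**What to change.** Amend the SAP as follows.

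1. **Anaemia-group comparisons, including Hb <100 g/L.** Define the cohort as intention-to-treat patients alive at the start of postoperative Day 3. Impute Day 3 haemoglobin only within that cohort. Report the number of deaths before Day 3 by randomised arm.
2. **Missing-data rule.** Reconcile Anaemia Group Definition with Statistical Analyses. Either impute unconditionally within the cohort, or keep the condition and state the method used when it is not met.
3. **Secondary aim.** Report deaths before Day 3 by arm and do not impute a haemoglobin for them. State that the comparison of arms is then conditional on survival to Day 3. Add a sensitivity analysis if these deaths are not negligible or are unbalanced between arms.

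The cost is SAP wording, with no new data. The anaemia-group cohort loses the few patients who died before Day 3. The secondary aim departs slightly from strict intention-to-treat, because survival to Day 3 is a post-randomisation event. A patient who dies during Day 3 before a sample is taken would still be imputed, which is a smaller version of the same problem.
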